3.2 Secondary Objectives

To provide evidence that endovascular reperfusion with Trevo is associated with a significant reduction in median infarct size compared to the control group at 24 (-6/+24) hours post randomization.

4 Study Endpoints and Safety Outcomes

The following clinical endpoints and safety outcomes will be evaluated in all subjects who are randomized whether or not the randomized study treatment is successfully administered, also called the Intent to Treat (ITT) group of subjects.

4.1 **Primary Endpoint**

The primary endpoint is the 90-day clinical outcomes assessed by the modified Rankin scale (mRS).

Document Number: CDM10000146

The primary endpoint analysis will consist of a comparison of the difference in proportion of functional independence (mRS 0-2) at 90 days post randomization between the active and control arm (dichotomous analysis) as well as the difference between the average weighted modified Rankin Scale (mRS) score at 90 days post randomization between the active and control groups (weighted mRS analysis). For the latter, each mRS category is assigned a numerical value representing its clinical utility, based on the work by Rivero-Arias, et al and Hong and Saver, as described in the Adaptive Design Plan in **Appendix F**. [48-49]

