7.8 Day 5-7 / Discharge

The subject may be discharged from the hospital when clinically stable, at the Investigator's discretion. The following data will be collected between Day 5-7 (if subject remains in the hospital) or prior to discharge, whichever is earlier:

- In hospital medical management details
- NIHSS
- mRS (blinded assessor)
- Repeat imaging MRI T2 Flair is not required but may be performed to re-assess final core infarct volume, at the treating physician's discretion, per local practice. CT may be performed if MRI is contra-indicated. If performed, this imaging will be collected and reviewed by the Core Lab.
- Adverse events and any treatment administered
- Subject disposition

For all subjects who remain in hospital after the Day 5-7 assessments, adverse events and any treatment administered will also be recorded through Discharge. For all subjects who expire prior to the Day 5-7/Discharge assessment, available information regarding the primary cause of death and date/time of death will be recorded, as well as whether the subject was made "do not resuscitate" (DNR) or "comfort care only" prior to expiration.

Deaths MUST be reported to Stryker NV within 24 hours of becoming aware, preferably by CRF completion. In the event that the EDC system is unavailable a written report by e-mail or fax is acceptable.

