4.8. Eligibility of Subjects, Exclusions, and Missing Data

Based on previous experiences in clinical trials of acute stroke, minimal loss to follow-up (LTFU) is expected for the 90-day assessment of the primary outcome measure. In the MERCI study, 7.2% (11/151) of subjects were LTFU, in Multi MERCI 2.4% (4/164) were LTFU, and in the TREVO 2 study, 3.4% (6/178) were LTFU. All efforts should be made to ensure near complete follow-up, with particular focus on the assessment of the primary outcome (mRS at 90 days) and mortality.

Nevertheless, some missing data may still occur. All randomized subjects will be included in the primary endpoint analysis (ITT). In case of missing 90-day mRS values, the 30-day mRS values will be incorporated into a multiple imputation model. In case of missing 90-day and missing 30-day mRS values, multiple imputation models will incorporate the day 5-7mRS; if that also missing, the subject will be counted as a failure (mRS 6). For conventional statistical analysis of the 90 day mRS and descriptive statistics (e.g. distribution of of mRS) will use LOCF of 30 day data. Refer to the adaptive design plan for details in Appendix F of study protocol.

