4.10. Analysis Populations

Intent-to-Treat (ITT): Includes all enrolled/randomized subjects. All randomized subjects will be included in the ITT analysis, where the arm classification is based on the randomized arm, even if they never receive it or receive treatment with another procedure. If the final analysis is only on the enriched population (refer to adaptive design plan in Appendix F of study protocol) then only those subjects in the enriched group will be included in the final analysis, based in ITT. This population is the primary population for all efficacy parameters.

As-Treated Analysis (AT): The same as the ITT population except subjects are analyzed based upon actual treatment received. Subjects who receive only medical therapy are included in the control arm, and subjects who receive any device-based therapy are included in the Trevo arm.

Per-Protocol (PP): A subset of the intent-to-treat population, including subjects who did not violate the inclusion/exclusion criteria or experience significant protocol deviations.

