4.15.5. Analysis of Secondary Effectiveness Endpoints

The analysis population to prove the efficacy of the Trevo® Retriever consists of two arms: Treatment arm and Control arm. The two arms are defined as below.

- a. Treatment arm: the subjects who are randomized to the Trevo thrombectomy plus medical management.
- b. Control arm: the subjects who are randomized to the medical management alone.

The following Secondary Effectiveness Endpoints will be analyzed:

Both Arms:

Stryker Neurovascular

Document Title: DAWN™ Trial Statistical Analysis Plan

Document Number: CDM10000704

Rev: AB

- Proportion of subjects with “early response” at Day 5-7/Discharge (whichever is earlier), defined as a NIHSS drop of ≥ 10 points from baseline or NIHSS score 0 or 1 will be presented by providing the count and percentage for each treatment arm. The difference in the percentage between two arms and the 95% CI for the difference will be calculated using the normal approximation to binomial. P-values will be calculated by the Chi-squared test or Fisher’s exact test as appropriate. Relative Risk (RR) was provided as Trevo thrombectomy plus medical management / medical management.
- Difference in all-cause mortality rates between the two arms and the 95% CI for the difference will be calculated using the normal approximation to binomial. P-values will be calculated by the Chi-squared test or Fisher’s exact test as appropriate. Relative Risk (RR) was provided as Trevo thrombectomy plus medical management / medical management.
- Difference in median final infarct size at 24 (-6/+24) hours from randomization, by MRI T2/Flair or CT (if contraindicated for MR) will be presented with n, mean, median, interquartile, standard deviation, minimum, and maximum between two treatment arms. P-values will be calculated with t-test assuming un-equal variances to compare the difference between two treatment arms.
- Difference in revascularization rates at 24 (-6/+24) hours from randomization, by CT-MR core lab assessment of vessel patency on CTA/MRA between the two arms and the 95% CI for the difference will be calculated using the normal approximation to binomial. P-values will be calculated by the Chi-squared test or Fisher’s exact test as appropriate. Relative Risk (RR) was provided as Trevo thrombectomy plus medical management / medical management.

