STRYKER CONFIDENTIAL - THIS DOCUMENT CONTAINS CONFIDENTIAL AND PROPRIETARY INFORMATION THAT IS THE PROPERTY OF STRYKER CORPORATION. NEITHER THIS DOCUMENT NOR THE INFORMATION HEREIN MAY BE REPRODUCED, USED, OR DISCLOSED TO ANY THIRD PARTY WITHOUT THE PRIOR WRITTEN CONSENT OF STRYKER CORPORATION

Treatment Arm Only:

Analysis of vessel reperfusion rates, by angiography measurement of modified TIC1 > 2b will be consistently reported with the count, rate and exact Clopper-Pearson 95% CI separately by post device and post procedure in treatment arm.

The enriched populations will be employed for secondary effectiveness endpoints analysis (refer to adaptive design plan in Appendix F of study protocol).

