6.2. Methods for Handling Missing Data Especially the AE Start Date

Handling of dropouts and missing data will depend on their frequency and the nature of the outcome measures. The distribution of prognostic factors between Subjects with and without data will be examined. This is used as a preliminary approach to assess whether or not missing data occurs randomly. Imputation for missing data is deemed necessary if missing data is associated with key prognostic factors and >20% of values of that variable are missing. Sensitivity analyses will be conducted to assess the impact of different assumptions on interpretation of the results. Outlier values will be examined for their validity; all data will be included. Any value judged to be invalid will be queried.

For the purposes of determining time to Adverse Event, missing and partial dates will be handled as follows. If the entire adverse event start date is missing then the procedure date will be used for the start date. If the month and the day of the month are missing but the year is available and the year is the same as the year of the procedure then the procedure date will be used for the start date. If the year is greater than the year of the procedure then January 1st will be used for the month and day of the start date. If the day is missing, but the month and year are available, then the 1st day of the month will be used as the day of the start date unless the imputed date would occur before the procedure in which case the procedure date will be used for the start date of the adverse event.

Note: With the exception of following special cases, this conservative scheme ensures that an AE with a partially or completely missing start-date will be treated as post-procedural.

Special Cases on Missing AE Start-dates

Using the above rules for the handling of missing AE start-dates, if the assumed AE start-date:

- is later than the reported AE stop-date, the assumed AE start-date will be reset and assumed to be the AE stop-date.
- If, based on the above rules, it cannot be determined whether the AE was taken prior to the study procedure, it will be assumed to be post-procedural.

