6.3. Rules for Calculating Rates and Handling Denominators

For Safety events, binary rates will be calculated using as a denominator as the number of all Subjects in the study, regardless of their follow-up time.

Stryker Neurovascular

Document Title: DAWN™ Trial Statistical Analysis Plan

Document Number: CDM10000704

Rev: AB

Other binary rates such as mRS or NIHSS will be calculated using a denominator as the total number of the available data for the outcome, excluding missing values.

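### SAP 6.3 takes NIHSS rates over available data and no rule scores a death before the Day 5-7/discharge NIHSS, so early deaths would drop out of the early-response comparison

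*SAP*

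**What the plan says.** SAP 3.1.2 defines early response as a fall of at least 10 NIHSS points from baseline, or a score of 0 or 1, at Day 5-7 or discharge. SAP 4.15.5 reports it by arm ("or NIHSS score 0 or 1 will be presented by providing the count and percentage for each treatment arm") with a difference, 95% CI, p-value and relative risk. For the population it says: "The enriched populations will be employed for secondary effectiveness endpoints analysis".

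SAP 6.3 sets two denominators. Safety events use all subjects. For the remaining binary rates, the text reads: "mRS or NIHSS will be calculated using a denominator as the total number of the available data for the outcome, excluding missing values".

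Protocol 7.8 foresees deaths before the assessment and has the circumstances recorded: "For all subjects who expire prior to the Day 5-7/Discharge assessment, available information regarding the primary cause of death and date/time of death". It assigns no score. Protocol Appendix B gives the NIHSS a range of 0 to 42, with no value for death.

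Three other places bear on the point:
- Protocol section 4 says that endpoints "will be evaluated in all subjects who are randomized whether or not the randomized study treatment is successfully administered". SAP 4.10 says "All randomized subjects will be included in the ITT analysis" and makes ITT the primary population for efficacy.
- SAP 4.8 has a failure rule, but for mRS only: a subject with no 90-day, 30-day or Day 5-7 mRS counts as mRS 6.
- SAP 6.2 calls imputation necessary "if missing data is associated with key prognostic factors and >20% of values of that variable are missing". It also promises sensitivity analyses, without naming a method or mentioning death.

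**The concern.** A subject who dies before the assessment has no NIHSS at that visit. An analyst who follows 6.3 will treat the value as missing and take the subject out of the denominator, together with any living subject whose NIHSS was not recorded. The comparison is then between survivors with a score, and survival to Day 5-7 may itself be changed by thrombectomy. If Trevo lowers early mortality, the reported relative risk understates its benefit compared with a count over all randomized subjects. If Trevo raises early mortality, the relative risk hides part of the harm. Reporting mortality separately does not correct the early-response result, which carries its own p-value and interval. Because 4.15.5 asks only for a count and percentage, the other possibility is that the rule is chosen once the data are in hand.

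**Working it through.** The documents state no rate, power or sample size for early response, so there is no planned figure to reproduce. The maximum of 250 per arm comes from SAP section 3, and the control mRS 6 proportion of 0.19 from SAP Table 1. All early death and response rates below are assumptions.

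**1. Does the SAP 6.2 trigger catch these deaths?** More than 20% of 500 means more than 0.20 x 500 = 100 missing values. If the planned 19% control mortality at Day 90 applied to both arms, and every death came before Day 5-7, there would be 0.19 x 500 = 95. Deaths alone would not reach the trigger even in that extreme case. Missing values in living subjects could add to the count, but no method would then be named.

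**2. Effect on the rates.** Let r be the response rate among all randomized and d the early death rate. The available-case rate is r/(1 - d). With r equal in both arms:

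| Early deaths | r | Available-case rates | Shift in difference |
|---|---|---|---|
| 5% v 2.5% | 20% | 0.20/0.95 = 21.05%; 0.20/0.975 = 20.51% | 0.54 points |
| 5% v 2.5% | 30% | 0.30/0.95 = 31.58%; 0.30/0.975 = 30.77% | 0.81 points |
| 10% v 5% | 20% | 0.20/0.90 = 22.22%; 0.20/0.95 = 21.05% | 1.17 points |
| 10% v 5% | 30% | 0.30/0.90 = 33.33%; 0.30/0.95 = 31.58% | 1.75 points |

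**3. Effect on the relative risk.** Trevo/control is multiplied by (1 - d_control)/(1 - d_Trevo), whatever the response rates.
- 5% v 2.5%: 0.95/0.975 = 0.97 if control has more deaths, 1.03 if Trevo has.
- 10% v 5%: 0.90/0.95 = 0.95, or 1.06.
- Equal deaths: 1.00.

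**4. Effect on the test.** With n = 250(1 - d) per arm and true response equal among all randomized, the two-sided 5% test rejects with probability Φ(-1.96 + δ/SE) + Φ(-1.96 - δ/SE). For 10% v 5% and r = 30%, n is 225 and 237.5. SE = √(0.3333 x 0.6667/225 + 0.3158 x 0.6842/237.5) = 4.36 points, and δ/SE = 1.75/4.36 = 0.40, giving 6.9%. For r = 20% (SE 3.83) it is 6.1%. For 5% v 2.5% it is 5.2-5.4%.

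**5. When response differs between arms.** The shift in the difference is r_T d_T/(1 - d_T) - r_C d_C/(1 - d_C), with T for Trevo and C for control. Take response of 30% v 20% and deaths of 10% on Trevo v 12% on control. The all-randomized difference is 10.0 points. The available-case difference is 0.30/0.90 - 0.20/0.88 = 33.3% - 22.7% = 10.6 points, a move towards the arm with fewer deaths. The relative risk still moves the other way, from 1.50 to 1.50 x 0.88/0.90 = 1.47.

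**6. A stress case.** The documents do not suggest an imbalance this large; it shows only what the rule could do. With 75 v 50 responders out of 250 each (30% v 20%), p = 0.0098 over all randomized. If early deaths are 5% on Trevo and 15% on control, the rates are 75/238 = 31.5% v 50/212 = 23.6%, p = 0.061. With the deaths reversed they are 75/212 = 35.4% v 50/238 = 21.0%, p = 0.0007.

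**The case against.** The best reply is that 6.3 excludes missing values and nowhere calls death a missing value. SAP 4.9 even classes a known death before Day 90 as a completed subject, and ITT is the primary efficacy population. A programmer could read an early death as a known non-responder. This stands in part: the SAP is silent, and a reader should not infer that it expressly excludes deaths. But completion is a disposition label and supplies no NIHSS, and 6.3 is the only specific denominator rule for this rate. Dropping the subject is therefore the more natural reading.

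A reader might also infer that 6.3 flatly contradicts Protocol section 4 and SAP 4.10. It does not. Those passages concern treatment delivery and arm assignment, and neither says how to count a subject without an outcome. The mismatch is with the intent of ITT.

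Nor does the rule favour the arm with more deaths on every measure. Step 5 shows the risk difference moving the other way, so only the statement about the relative risk is general.

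Finally, the effect is modest, the documents assign no alpha to secondary endpoints, and mortality is reported by arm. All of that is right and limits the weight of the point. The sensitivity analyses in 6.2 could include death as non-response, but nothing commits to it. Appendix F was not in the text available for this review; the documents cite it for the mRS analyses and the enriched population, not for NIHSS.

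**Conclusion.** The gap is real and the consequence is probably small. On its natural reading, 6.3 conditions the early-response comparison on surviving to the assessment, and no other rule in the documents prevents this. At 250 per arm with equal response of 20-30%, early death imbalances of 2.5 to 5 points shift the difference by 0.5-1.8 points, against standard errors of 3.7-4.4 points. They move the relative risk to between 0.95 and 1.06. The true size and direction cannot be known, because neither document gives early death or response rates by arm.

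A reader might infer that the trial's conclusion is at risk, or that the rule is tilted towards Trevo. Neither follows. The co-primary mRS analyses have their own missing-data rules, study success does not depend on this endpoint, and the relative risk moves against Trevo if Trevo lowers early mortality.

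**What to change.** Amend SAP 6.3 and 4.15.5, before data lock, so that for early response:
1. the denominator is all ITT subjects, or the enriched ITT population if enrichment occurs;
2. death before the Day 5-7/discharge NIHSS counts as non-response;
3. one rule is prespecified for a living subject with no NIHSS at that visit, for example non-response;
4. the available-case rate is reported as a sensitivity analysis.

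Item 3 needs a stated choice because alternatives give different rates. If 2-5% of subjects were alive without a score and 20-30% of those were responders on their last NIHSS (both assumed), scoring them as non-response instead of carrying that value forward lowers the rate by 0.02 x 0.20 = 0.4 to 0.05 x 0.30 = 1.5 points. Carrying the 24-hour NIHSS forward is an option, but it changes the time point assessed.

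The cost is a few sentences and one table row. No new data are needed, since date and cause of death are already recorded. The price is interpretive: early response becomes a composite in which death counts as failure, and the report should say so.

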7. STATISTICAL REPORT TEMPLATE

The report template will be established prior to database lock.

9. LIST OF ABBREVIATIONS AND DEFINITION OF TERMS

TABLE 4. ADVERSE EVENT DEFINITIONS AND CLASSIFICATION

Abbreviation	Full Term
ACA	Anterior Cerebral Artery
ADC	Apparent Diffusion Co-efficient
ADP	Adaptive Design Plan
AE	Adverse Event
AHA	American Heart Association
AIS	Acute Ischemic Stroke
AOL	Arterial Occlusive Lesion
ASA	American Stroke Association
AT	As Treated
CA	Competent Authority
CEC	Clinical Events Committee
CIM	Clinical Imaging Mismatch
CRF	Case Report Form

STRYKER CONFIDENTIAL - THIS DOCUMENT CONTAINS CONFIDENTIAL AND PROPRIETARY INFORMATION THAT IS THE PROPERTY OF STRYKER CORPORATION. NEITHER THIS DOCUMENT NOR THE INFORMATION HEREIN MAY BE REPRODUCED, USED, OR DISCLOSED TO ANY THIRD PARTY WITHOUT THE PRIOR WRITTEN CONSENT OF STRYKER CORPORATION

Stryker Neurovascular

Document Title: DAWN™ Trial Statistical Analysis Plan

Document Number: CDM10000704

Rev: AB

Abbreviation	Full Term
CT	Computerized Tomography
CTA	Computerized Tomography Angiography
CTP	Computerized Tomography Perfusion
DBP	Diastolic Blood Pressure
DE	Distal Embolization
DMC	Data Monitoring Committee
DNR	Do Not Resuscitate
DRSAE	Device-related SAE
DWI	Diffusion Weighted Imaging
EC	Ethics Committee
EE	Efficacy Evaluable
ENT	Embolization to New Territory
ESO	European Stroke Organization
GCP	Good Clinical Practice
HCT	Hematocrit
HI-I	Petechial hemorrhage type I
HI-II	Petechial hemorrhage type II
Hr/Hrs	Hour/Hours
IA	Intra-Arterial
ICA	Internal Carotid Artery
ICA-T	Internal Carotid Artery Terminus
ICF	Informed Consent Form
ICH	Intracranial Hemorrhage
IFU	Instructions For Use
INR	International Normalized Ratio
IRB	Institutional Review Board
ITT	Intent-To-Treat
IV	Intravenous
IVH	Intraventricular Hemorrhage

STRYKER CONFIDENTIAL - THIS DOCUMENT CONTAINS CONFIDENTIAL AND PROPRIETARY INFORMATION THAT IS THE PROPERTY OF STRYKER CORPORATION. NEITHER THIS DOCUMENT NOR THE INFORMATION HEREIN MAY BE REPRODUCED, USED, OR DISCLOSED TO ANY THIRD PARTY WITHOUT THE PRIOR WRITTEN CONSENT OF STRYKER CORPORATION

Stryker Neurovascular

Document Title: DAWN™ Trial Statistical Analysis Plan

Document Number: CDM10000704

Rev: AB

Abbreviation	Full Term
IVRS/IWRS	Interactive Voice Response System / Interactive Web Response System
LAR	Legally Authorized Representative
LTFU	Lost To Follow Up
LVO	Large Vessel Occlusion
M-1	the initial horizontal segment of the MCA, prior to the first bifurcation or trifurcation
M-2	the portions of the MCA distal to the first bifurcation or trifurcation, but prior to the second bifurcation
MCA	Middle Cerebral Artery
MR/MRI	Magnetic Resonance / Magnetic Resonance Imaging
MRA	Magnetic Resonance Angiography
mRS	Modified Rankin Scale
mTICI	Modified Thrombolysis in Cerebral Infarction
NIHSS	National Institute of Health Stroke Scale
PH-I	Parenchymal hemorrhage type 1
PH-II	Parenchymal hemorrhage type 2
PP	Per Protocol
PRSAE	Procedure-related SAE
PT	Prothrombin Time
PTT	Partial Thromboplastin Time
PWI	Perfusion Weighted Imaging
rCBF	Relative Cerebral Blood Flow
RIH	Remote Intracerebral Hemorrhage
SAE	Serious Adverse Event
SADE	Serious Adverse Device Effect
SAH	Subarachnoid Hemorrhage
SBP	Systolic Blood Pressure
SICH	Symptomatic Intracranial Hemorrhage
TICI	Thrombolysis in Cerebral Infarction
TIMI	Thrombolysis in Myocardial Infarction

STRYKER CONFIDENTIAL - THIS DOCUMENT CONTAINS CONFIDENTIAL AND PROPRIETARY INFORMATION THAT IS THE PROPERTY OF STRYKER CORPORATION. NEITHER THIS DOCUMENT NOR THE INFORMATION HEREIN MAY BE REPRODUCED, USED, OR DISCLOSED TO ANY THIRD PARTY WITHOUT THE PRIOR WRITTEN CONSENT OF STRYKER CORPORATION

Stryker Neurovascular

Document Title: DAWN™ Trial Statistical Analysis Plan

Document Number: CDM10000704

Rev: AB

Abbreviation	Full Term
TLSW	Time Last Seen Well
tPA	Tissue Plasminogen Activator (alteplase)
UADE	Unanticipated Adverse Device Effect
UK	Urokinase
USADE	Unanticipated Serious Adverse Device Effect
WUS	Wake Up Stroke

STRYKER CONFIDENTIAL - THIS DOCUMENT CONTAINS CONFIDENTIAL AND PROPRIETARY INFORMATION THAT IS THE PROPERTY OF STRYKER CORPORATION. NEITHER THIS DOCUMENT NOR THE INFORMATION HEREIN MAY BE REPRODUCED, USED, OR DISCLOSED TO ANY THIRD PARTY WITHOUT THE PRIOR WRITTEN CONSENT OF STRYKER CORPORATION
